11.2 Monitoring Procedures

The Clinical Trial Monitor will contact and/or visit the investigator site periodically to verify the adherence to the protocol, the maintenance of trial-related source records, and the completeness and accuracy of all eCRF entries compared to source data. The investigator will cooperate with the trial monitor to ensure that any discrepancies that may be identified are resolved.

11.3 Audit and Inspection

The investigator will make all the trial-related source data and records available to a quality assurance auditor mandated by the sponsor, or to domestic or foreign regulatory inspectors, after reasonable notice. The main purposes of an audit or inspection are to confirm that the rights and well-being of the subjects have been adequately protected, and that all data relevant for the evaluation of the IP have been processed and reported in compliance with GCP/ICH and applicable regulatory requirements.

The investigator is to notify the MC2 or designee immediately of any inspection by regulatory authorities or IRBs.

12.0 ETHICS

12.1 Ethical Conduct of the Trial

This trial must be carried out in compliance with the protocol and the applicable laws and regulatory requirements of the appropriate regulatory agency. The trial must be conducted in accordance with the ethical principles originating from the Declaration of Helsinki and amendments and the ICH-GCP guidelines.

12.2 Institutional Review Board (IRB) or Independent Ethics Committee (IEC)

This protocol, the proposed informed consent form, and other information for subjects must be reviewed and approved by an IRB or IEC, before the start of the trial, in compliance with local regulations. This committee must also approve any amendments to the protocol, other than administrative ones, before initiation of the amendment procedures.

12.3 Subject Information and Consent

Before participation in the trial, each subject is required to provide written consent to participate in the trial. No trial-specific procedures will be performed before a subject's informed consent is obtained.

12.4 Disclosure and Confidentiality

12.4.1 Confidentiality of trial documentation

By signing the protocol, the investigator agrees to keep all information provided by the sponsor in strict confidence and to request similar confidentiality from his/her staff and the IRB or IEC. Trial

documents provided by the trial sponsor (i.e., protocols, Investigators' Brochures, eCRFs and other material) will be stored appropriately to ensure their confidentiality. The information provided by the sponsor to the investigator may not be disclosed to others without direct written authorisation from the sponsor, except to the extent necessary to obtain informed consent from subjects who wish to participate in the trial.

12.4.2 Privacy of individual health information

The investigator will undertake to protect the privacy of all individually identifiable health information except as specifically authorised by each individual subject through the written informed consent. The Informed Consent document will include a request of the subject's consent to release the collected data for research purposes in such a way that the individual's identity remains masked. While all data records will be identified by the corresponding subject number, the identity of the subject will be held in confidential source documents at the trial site. All trial personnel with access to this information are legally bound not to disclose such information.

13.0 EMERGENCY PROCEDURES

13.1 Emergency Unblinding

Un-blinding by trial personnel should be performed only in emergencies where knowledge of the subject's treatment assignment is essential for further management of the subject's medical care. Un-blinding a subject's treatment assignment under any other circumstances will be considered a protocol violation.

The investigator should assess the relationship of any AEs to administration of the IP prior to unblinding.

The investigator is strongly encouraged to contact the trial Medical Expert before un-blinding any subject's treatment assignment but must do so within 1 working day after the un-blinding. The subject's treatment code should not be communicated to the Medical Expert. The un-blinding will be documented by the investigator.

If the blind is broken for any reason, the investigator must record the date and reason for breaking the blind on the appropriate trial documents.

14.0 INSURANCE

MC2 has taken out appropriate insurance policies covering the subjects in the clinical trial in accordance with applicable laws and regulations.

MC2 Therapeutics

Confidential

15.0 PUBLICATION POLICY

The clinical trial information will be posted on www.clinical trial.gov and in accordance with applicable regulations.

All publications (e.g., manuscripts, abstracts, oral/slide presentations, book chapters) based on this trial must be submitted to MC2 for review, as specified in the Clinical Trial Agreement between the institution, investigator and MC2 or its designee.

MC2-01-C7

SAS®	Statistical Analysis System®
SAS/STAT®	SAS® Statistics software module
SD	Standard deviation
SDTM	Standard Data Tabulation Model
SGA	Subject global assessment of disease severity
SOC	System Organ Class
TFL	Tables, figures, listings
TPA	Tipping-point analysis
VAS	Visual analogue scale

List of Abbreviations and Acronyms

1 Introduction

The Phase III trial MC2-01-C7 will be analyzed and reported in accordance with the clinical trial protocol (CTP) [1] and the International Conference on Harmonization (ICH) guidelines ICH E3 [2], ICH E6 [3] and ICH E9 [4]. MC2-01-C7 is a trial to compare the MC2 product in psoriasis vulgaris with a vehicle and an active comparator focusing on psoriasis on the body (trunk and/or limbs).

This statistical analysis plan (SAP) should be read in conjunction with the CTP and the electronic case report form (CRF) [5]. This version of the plan has been developed using the CTP version 2.0 dated 16 October 2018 and the SDTM-annotated CRF dated 15 August 2019. Any further changes to the protocol or CRF may necessitate updates to the SAP.

Based on this SAP, deliverables are derived analysis datasets following the CDISC ADaM standard, tables, figures and listings (TFL).

2 Study Design and Objectives

2.1 Study Design

This is a prospective, investigational, investigator-blind, vehicle and active-controlled, parallel-group, 3arm, randomized, phase-III trial conducted at approximately 34 sites in the European Union. The trial population consists of subjects fulfilling all inclusion and no exclusion criteria as defined in the CTP, Sections 5.2 and 5.3 with any exceptions documented [1]. Random allocation to one of three parallel treatment groups in a 3:1:3 ratio (MC2-01 cream; MC2-01 vehicle; active comparator) is stratified by site.

A total of 476 subjects are planned to be enrolled, randomized and observed until final evaluation and completion. Subjects prematurely terminating the trial will not be replaced.

The maximum trial duration for each subject will be approximately 14 weeks and includes a screening period of up to 30 days (if washout of prohibited medications is required), an 8-week treatment period, and a follow-up period of 2 weeks.

A total of seven visits and a telephone interview of subjects are planned. The telephone interview is planned for Week 2 (Visit 3), while the visits will be held at screening (Visit 0, Day -30 to 0), randomization (Visit 1, Week 0, Day 0), Visits 2, 4, and 5 at Weeks 1, 4 and 6, respectively, planned for Days 7, 28, and 42 plus/minus 2 days, respectively, Visit 6 as end of treatment Visit (Week 8, Day 56+/-2, or at early termination), and Visit 7 as follow-up visit (Week 10, Day 70+/-2). The follow-up visit is planned as an on-site visit in case of abnormal laboratory values or unresolved adverse events (AE). Otherwise, the follow-up visit is a telephone interview. At any time during the trial, if judged necessary by the investigator, unscheduled visits may be performed. For a visit schedule, see CTP Section 7.0 [1].

2.2 Treatments, Study Groups and Treatment Assignment

Subjects will be randomly allocated to either receive *MC2-01 cream*, a combination product of calcipotriol and betamethasone, a *MC2-01 vehicle* or an *active comparator*, a marketed calcipotriol and betamethasone gel/topical suspension. Subjects apply the investigational product (IP) topically once daily preferable in the evening for 8 weeks to affected areas on the trunk (including the neck), the limbs, i.e., arms (including the back of the hands), the legs (including the buttocks and the top of the feet) and the scalp.

Subjects should apply enough IP to treat the entire affected areas. Up to 4 tubes/bottles of 60 gram will be dispensed for a treatment period of 2 weeks including the allowed visit window of 2 days. The weekly dose is not to exceed 100 g, and the treated area should not exceed 30% of the body surface area (BSA).

Subjects classified as *clear* at any of the on-treatment visits may stop the IP treatment at the investigator's discretion. They should remain in the trial and attend all visits up to and including the follow-up visit. The IPs will continue to be dispensed to the subject, and IP treatment may be restarted at the subject's discretion. The subjects should not discontinue IP treatment themselves between visits but are only allowed to stop using the IP treatment on the advice of the investigator at a scheduled visit.

Subjects will be uniquely identified by a five-digit subject number composed of a two-digit site number, followed by three digits. The investigators and the entire study team will be kept blinded to treatment allocation information until the time of unblinding. Due to difference in formulation and packaging, it is not possible to double blind the IPs. A designated non-blinded staff member will be responsible for handling the IP (e.g. dispensing, returning, drug accountability). The investigators and the rest of the blinded study team will be kept blinded to treatment formulation until the time of unblinding.

2.3 Study Objectives

2.3.1 Primary Objectives

The primary objective is to evaluate the efficacy of MC2-01 cream compared to active comparator in subjects with psoriasis vulgaris.

2.3.2 Secondary Objectives

The secondary objective is to characterise the safety profile of MC2-01 cream in subjects with psoriasis vulgaris.

2.4 Study Endpoints

In the following, endpoints are described by label, and by unit or valid categories. A categorical endpoint is of yes-no-type, if no categories are specified. A continuous or numerical endpoint is a score with or without a unit, if no unit is specified.

2.4.1 Efficacy Including Subject-Reported Outcomes

The primary endpoint is the percentage change from baseline in the modified Psoriasis Area and Severity Index (mPASI) on the body (trunk and/or limbs) at Week 8.

Based on a physician's global assessment (PGA) and the Psoriasis Treatment Convenience Scale (PTCS), secondary endpoints include

- *PGA success* on the body at Week 8, defined as a minimum 2-point decrease from baseline to Week 8 on the PGA of psoriasis severity on the body (trunk and/or limbs) to a PGA of psoriasis severity of 0 (clear) or 1 (almost clear); i.e., a score of 0 (clear) or 1 (almost clear) for subjects with moderate disease at baseline; or a score of 0 (clear) for subjects with mild disease at baseline.
- Subject assessment of treatment convenience at Week 8 using the PTCS total score,
- Number of subjects with at least 75% reduction in mPASI from baseline (mPASI 75) on the body (trunk and/or limbs) at Week 8.
- *PGA success* on the scalp at Week 8, defined as a minimum 2-point decrease from baseline to Week 8 on the PGA of psoriasis severity on the scalp to a PGA of psoriasis severity of 0 (clear) or 1 (almost clear); i.e., a score of 0 (clear) or 1 (almost clear) for subjects with severe or moderate disease at baseline; or a score of 0 (clear) for subjects with mild disease at baseline.

Primary and secondary endpoints will be evaluated confirmatorily by hierarchical testing as described in Sections 5.2 and 5.3 below. Other endpoints will be exploratorily analyzed.

Other endpoints include

- Percentage change from baseline in mPASI score on the body (trunk and/or limbs) at Week 4,
- mPASI 75 on the body (trunk and/or limbs) at Week 4,
- PGA success on the body at Week 4,
- PGA success on the scalp at Week 4,
- Change from baseline in Subject Global Assessment (SGA) at Week 4 and Week 8,
- Subject assessment of treatment convenience at Week 4 using the PTCS total score,
- Change from baseline in the Dermatology Life Quality Index (DLQI) score at Week 4 and Week 8,
- Change from baseline in EQ-VAS at Week 4 and Week 8,
- BSA involvement on the body and on the scalp at Week 4 and Week 8.

mPASI and mPASI 75

At all on-site visits (Screening, Week 0, Week 1, Week 4, Week 6, Week 8, and Early Termination), the investigator will assess the extent and severity of the subjects' psoriasis on the body (trunk and/or limbs) using an mPASI scoring system for each of the 3 areas (arms, trunk, and legs). The extent (E) is scored 0 to 6. The severity of the psoriatic lesions in each of the 3 areas will be recorded for each of the signs of redness (R), thickness (T), and scaliness (S). For each clinical sign, a single score, reflecting the average severity of all psoriatic lesions on given body region, will be determined. Redness, thickness and scaliness scores are ranging from 0 to 4. The meaning of scores is summarized in the following table.

Extent (E) Redness (R) Thickness (T) Scaliness (S) Score 0 no involvement none (no erythema) none (no plaque none (no scaling) elevation) <10% mild (slight, barely 1 mild (faint erythema, mild (sparse, finepink to very light red) scale lesions, only perceptible elevation) partially covered) 2 10% to 29% moderate (definite moderate (definite moderate (coarser light red erythema) elevation but not scales, most of thick) lesions covered) 3 30% to 49% severe (dark red severe (definite severe (entire lesion elevation, thick covered with coarse erythema) plaque with sharp scales) edge) 4 50% to 69% very severe (very very severe (very very severe (very dark red erythema) thick plaque with thick coarse scales, possibly fissured) sharp edge) 5 70% to 89% 6 90% to 100%

Table 1: Overview of the meaning of mPASI scores assessed for arms, trunk and legs

Per area, the scores for extent, redness, thickness and scaliness are combined to $A = E \cdot (R+T+S)$. Ranging from a minimum score of 0 and a maximum score of 64.8, the mPASI is calculated from the scores of the extent and severity of the disease by use of the following equation:

 $mPASI = 0.2 \cdot A_{arms} + 0.3 \cdot A_{trunk} + 0.4 \cdot A_{legs}.$

At any post-baseline visit, mPASI 75 is defined as an indicator of a reduction in mPASI from baseline of 75% or more.

PGA and PGA Success on the Body and on the Scalp

PGA measures the investigator's impression of the disease at a single point using a defined, 5-point, static PGA scale (0 = clear, 1 = almost clear, 2 = mild, 3 = moderate or 4 = severe) at Screening, Weeks 0, 1, 4, 6, 8, and Early Termination.

The PGA assessment will be made separately for the body (trunk and/or limbs) and the scalp. It will represent the *average* lesion severity on the two body locations.

At any post-baseline visit, *PGA success* is defined as a minimum 2-point decrease from baseline to the respective visit on the PGA of psoriasis severity to 0 (clear) or 1 (almost clear).

PTCS

PTCS will be completed by the subjects before any other assessments are performed at Weeks 1, 4, 8, and Early Termination.

The aim of PTCS is to assess the impact and convenience of psoriasis treatment. The scale consists of 6 disease-specific, self-report questions rated on a 10-point scale ranging from 1 to 10. The questions are

- 1. How easy was the treatment to apply to the skin? Answered by 1 = very difficult to 10 = very easy.
- 2. How greasy was the treatment when applying it to the skin? Answered by 1 = very greasy to 10 = not greasy.
- 3. How moisturised did your skin feel after applying the treatment? Answered by 1 = not moisturized to 10 = very moisturized.
- 4. How greasy did your skin feel after applying the treatment? Answered by 1 = very greasy to 10 = not greasy.
- 5. How much did treating your skin disrupt your daily routine? Answered by 1 = very disturbing to 10 = not disturbing.
- 6. Overall, how satisfied were you with the medical treatment? Answered by 1 = not satisfied to 10 = very satisfied.

Ranging from 5 to 50, a PTCS total score is the sum of the scores on questions 1 to 5. If no more than two questions are answered, the PTCS total score is missing. If one or two questions remain unanswered, the missing scores are replaced by the average of the answered scores for the summation.

SGA

Subjects will grade the overall severity of their symptoms according to the following 5-point scale at Weeks 0, 1, 4, 6, 8, and Early Termination:

0 =Clear; no psoriasis symptoms at all.

- 1 = Very mild; very slight psoriasis symptoms that do not interfere with daily life.
- 2 = Mild; slight psoriasis symptoms that interfere with daily life only occasionally.
- 3 = Moderate; definite psoriasis symptoms that interfere with daily life frequently.
- 4 = Severe; intense psoriasis symptoms that interfere or restrict daily life very frequently.

DLQI

The DLQI is a validated questionnaire consisting of 10 questions relating to the degree to which the subject's skin condition affected their daily activities, assessed at Weeks 0, 1, 4, 8, and Early Termination [6]. The questions are

- 1. Over the last week, how itchy, sore, painful or stinging has your skin been? Answered by 0 = not at all to 3 = very much.
- 2. Over the last week, how embarrassed or self-conscious have you been because of your skin? Answered by 0 = not at all to 3 = very much.
- 3. Over the last week, how much has your skin interfered with you going shopping or looking after your home or garden? Answered by 0 = not at all/not relevant to 3 = very much.
- 4. Over the last week, how much has your skin affected the clothes you wear? Answered by 0 = not at all/not relevant to 3 = very much.
- 5. Over the last week, how much has your skin affected any social or leisure activities? Answered by 0 = not at all/not relevant to 3 = very much.
- 6. Over the last week, how much has your skin made it difficult for you to do any sport? Answered by 0 = not at all/not relevant to 3 = very much.

- 7. Over the last week, has your skin prevented you from working or studying? Answered by no, 0 = not relevant or 3 = yes. If no, over the last week, how much has your skin been a problem at work or studying? Answered, by 2 = a lot, 1 = a little, 0 = not at all.
- 8. Over the last week, how much has your skin created problems with your partner or any of your close friends or relatives? Answered by 0 = not at all/not relevant to 3 = very much.
- 9. Over the last week, how much has your skin caused any sexual difficulties? Answered by 0 = not at all/not relevant to 3 = very much.
- 10. Over the last week, how much of a problem has the treatment for your skin been, for example by making your home messy, or by taking up time? Answered by 0 = not at all/not relevant to 3 = very much.

DLQI domain scores are defined as the sum of the scores on questions 1 and 2 as symptoms and feelings domain, questions 3 and 4 as daily activities domain, questions 5 and 6 as leisure domain, and questions 8 and 9 as personal relationships domain, respectively. Work and school domain is covered by question 7, treatment domain by question 10.

Ranging from 0 to 30, the DLQI score is the sum of the 10 scores. If one question remains unanswered, the missing score is replaced by 0 for the summation. If more than one question remains unanswered, the DLQI score is missing.

EQ-5D

The EQ-5D is intended to measure health-related quality of life (QOL) [7]. It consists of 5 items and a visual analogue scale (EQ-VAS). The EQ-VAS records the subject's perceptions of their own current overall health scoring in a range from 0 to 100. The 5 self-assessment questions describe the subject's current health in 5 dimensions i.e., mobility, self-care, usual activities, pain/discomfort, and anxiety/depression. The items follow a 5-point Likert scale.

BSA Involvement

BSA involvement will be determined on the body, on the scalp and total as the extent (percentage) of subject's psoriatic involvement on the total BSA at Week 0 (Day 0, Baseline), Week 4, Week 8, and at Early Termination.

2.4.2 Safety and Tolerability

Local Skin Reaction

Assessments of local skin reaction (LSR) will be performed by the investigator at all on-site post-screening visits. The treatment area and/or immediate surrounding for the following identified signs will be assessed:

- Perilesional erythema, scaling, edema, atrophy, vesicles and erosion/ulceration;
- Lesional vesicles, and erosion/ulceration.

The intensity of each local skin reaction category is to be graded according to the scale in the following table. The most severe intensity observed for each category of the local skin reaction assessment is recorded.

Category		Intensity			
Area	Sign	0 = absent	1 = mild	2 = moderate	3 = severe
Lesional	Erosion/ ulceration	none	barely visible erosion	distinct erosion	Ulceration
	Vesicles	none	barely visible vesicles	distinct vesicles	Bullae
Perilesional	Erythema	none	barely visible erythema	distinct erythema	dark red erythema
	Scaling	none	barely visible scaling	distinct scaling	gross scales
	Edema	none	barely visible swelling	easily palpable swelling	gross swelling
	Atrophy	none	barely visible thinning	distinct thinning	Striae
	Vesicles	none	barely visible vesicles	distinct vesicles	Bullae
	Erosion/	none	barely visible erosion	distinct erosion	Ulceration
	ulceration		-		

Table 2: Overview of intensity grading of local skin reaction by area and sign

An LSR sum score is defined as the sum of intensity grades across all areas and signs per visit. Per sign, the most intense reaction is defined as the maximum intensity grade across visits.

Adverse Events

All adverse events (AE) are recorded with the following attributes:

- severity (mild, moderate, severe),
- location of AE to treatment area,
- action taken (none, concomitant therapy, concomitant non-drug therapy),
- action taken with IP (dose not changed, dose reduced, dose increased, dose interrupted, drug withdrawn, not applicable, unknown, other)
- outcome (recovered, resolved with sequelae, recovering/ resolving, ongoing, death),
- withdrawal due to AE,
- start and end dates,
- relationship to IP (definitely related, probably related, possibly related, not related),
- relationship to study procedure,
- seriousness, criterion for seriousness (death, life-threatening, hospitalization, disability/incapacity, congenital anomaly/birth defect, other).

Any AE is treatment-emergent, if fulfilling the definition in Section 4.4.5.

Any AE is a drug-related AE, if relationship to IP is not assessed as *not related*.

Any AE is leading to drug withdrawal, if action taken with IP is *drug withdrawn*.

Any AE is located in the treatment area, if location of AE to treatment area is *inside treatment area* or *combined*.

Verbatim terms of the description of AEs will be coded according to MedDRA version 22.0 and classified according to preferred terms (PT) and primary system organ classes (SOC).

Laboratory Parameters

For all subjects, the following tests will be performed at Week 0 (Day 0, Baseline), Week 4 and Week 8, and at Early Termination:

- Serum biochemistry: serum calcium (albumin corrected), serum albumin, serum alkaline phosphatase, serum phosphate, plasma parathyroid hormone, 25-OH Vitamin D (only at Week 0).
- Urinalysis: urinary calcium, urinary phosphate, urinary calcium:creatinine ratio.

Laboratory parameters are reported in or converted to SI units [8]. According to normal ranges, laboratory values are categorized as *abnormal low*, *within normal range*, or *abnormal high*.

During the course of the trial, urine pregnancy tests will be performed at Screening, Week 0, Week 4, Week 8, and at Early Termination.

Vital Signs

Systolic and diastolic blood pressure, pulse rate and body temperature (oral or ear) will be measured at Week 0 (Day 0, Baseline), Week 4, Week 8, and at Early Termination. Values outside notable ranges will be flagged. For a definition of notable ranges, see Section 4.6.4 below.

Physical Examination

Abbreviated physical examination and complete dermatological examination will be assessed at Screening (Visit 0), Week 0 (Day 0, Baseline), Week 4, Week 8 and at Early Termination. In addition, height and weight are measured at Week 0 (baseline).

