8.7.2 Local Skin Reaction Assessment

Assessments of local skin reaction will be performed at all post-screening visits for all subjects in the trial. These local skin reaction assessments (LSRs) will be made by the investigator. The treatment area and the immediate surrounding area will be assessed.

The LSR sum score will be summarized by trial visit and treatment group. The LSR intensities, scored as 0=none, 1=mild, 2=moderate, or 3=severe, will be summarized by trial visit and treatment group for each of the LSR categories.

In addition, for each LSR category, the most intense reaction over the course of the trial will be determined for each subject, and the frequency distributions of these scores will be tabulated.

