4.4.2 Dates

The date of Visit 1 is the reference date, Day 0. Start and end dates, and the dates of last study drug application and last contact will be related to Day 0, given as *study day*. Negative study days indicate dates before Visit 1.

It is assumed that treatment in the treatment period occurs from the evening of Day 0 to the day before Visit 6 (Week 8) unless otherwise reported.

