4.4.3 Identification of Baseline Values

Per variable, baseline values are the values reported at randomization (Visit 1/Week 0, Day 0). If values at randomization are missing, values at Screening (Visit 0) are considered as baseline values.

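### As written, the most intense local skin reaction includes the pre-treatment Day 0 grade, which inflates the frequencies and dilutes arm differences in one descriptive table

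*SAP*

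**What the plan says.** SAP 2.4.2 sets the assessment times: "Assessments of local skin reaction (LSR) will be performed by the investigator at all on-site post-screening visits". Protocol 8.7.2 says the same for all subjects, and the LSR row of Protocol Table 7-1 is marked at Visit 1 (Day 0) and at Weeks 1, 4, 6 and 8/early termination.

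The summary rule in SAP 2.4.2 is: "Per sign, the most intense reaction is defined as the maximum intensity grade across visits". Protocol 8.7.2 is equally open: "for each LSR category, the most intense reaction over the course of the trial will be determined for each subject". Neither document limits the maximum to visits after the first application.

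On timing, SAP 4.4.2 assumes that "treatment in the treatment period occurs from the evening of Day 0 to the day before Visit 6", unless otherwise reported. SAP 4.4.3 takes Visit 1 (Day 0) as the baseline.

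The result is reported in Table 14.3.2.2. SAP 5.5.4 also plans by-visit summaries of LSR sum scores with changes from baseline, Table 14.3.2.1 summarises LSR assessments by visit, and Protocol 8.7.2 plans the intensities of each category by visit and arm.

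**The concern.** A worst-grade table of local reactions is normally read as what happened on treatment. Under the written rule, a subject with grade 2 perilesional erythema at Day 0 and grade 0 at every later visit appears as having a moderate reaction.

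This is at odds with the rest of the safety plan:

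- **Adverse events (SAP 4.4.5):** treatment-emergent only if they start or worsen at or after the first application.
- **Laboratory shifts (Protocol 8.7.3):** from baseline to the most extreme value after baseline.
- **Notable vital signs (SAP 4.6.4):** restricted to values after treatment.

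Only the LSR maximum has no such limit, which looks like an oversight rather than a choice.

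LSR is the first safety endpoint listed in Protocol 4.2. Protocol 8.7 names it as one of three main bases for assessing safety, and characterising the safety of the cream is the secondary objective. Table 14.3.2.2 is the only planned summary of each subject's worst LSR grade. Randomisation should balance Day 0 signs across arms, so counting them would not favour one arm systematically. It would raise every arm's frequency and pull the arms towards each other.

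**Working it through.** The plan states no figure on this point, so there is none to reproduce. The check has two parts.

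**1. Does the rule include a pre-treatment grade?**

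- LSR is graded at Visit 1 (Protocol Table 7-1; SAP 2.4.2).
- Visit 1 is Day 0, and treatment is taken to start that evening (SAP 4.4.2). The Visit 1 grade therefore precedes treatment.
- The maximum is over visits, without restriction (SAP 2.4.2; Protocol 8.7.2).

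Taken together, the Visit 1 grade is one of the grades over which the maximum is taken.

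**2. How much could it matter?**

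The documents give no LSR frequencies, so every input here is an assumption:

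- *b*: proportion of subjects with a given sign at Day 0, equal across arms by randomisation.
- *p*: proportion with a new on-treatment reaction, independent of Day 0 status; 6% in one arm and 3% in the other, a true ratio of 2.0.
- *r*: share of Day 0 signs that are gone at every later visit.

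Formulas for the proportion tabulated with any reaction:

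- All-visit maximum: 1 − (1 − b)(1 − p). The arm difference is (1 − b) times the true difference.
- Post-baseline maximum: 1 − (1 − s)(1 − p), where s = b(1 − r) is the proportion whose Day 0 sign persists.

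All-visit maximum:

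| b | Arm with p = 6% | Arm with p = 3% | Difference (points) | Ratio |
|---|---|---|---|---|
| 0% | 6.0% | 3.0% | 3.0 | 2.0 |
| 5% | 1 − 0.95 × 0.94 = 10.7% | 1 − 0.95 × 0.97 = 7.85% | 2.85 | 1.36 |
| 20% | 1 − 0.80 × 0.94 = 24.8% | 1 − 0.80 × 0.97 = 22.4% | 2.4 | 1.11 |
| 40% | 1 − 0.60 × 0.94 = 43.6% | 1 − 0.60 × 0.97 = 41.8% | 1.8 | 1.04 |

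Post-baseline maximum at b = 20%:

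- All Day 0 signs resolve (r = 1, s = 0): 6.0% versus 3.0%, ratio 2.0.
- Half resolve (r = 0.5, s = 10%): 1 − 0.90 × 0.94 = 15.4% versus 1 − 0.90 × 0.97 = 12.7%, ratio 1.21.
- None resolve (r = 0, s = 20%): 24.8% versus 22.4%, ratio 1.11, the same as the all-visit maximum.

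Two things follow. The dilution is larger on the ratio scale than on the absolute scale: at b = 20% the ratio falls from 2.0 to 1.11, while the difference falls from 3.0 to 2.4 points. And restricting the maximum to later visits removes only the Day 0 signs that resolve. Persistent ones stay in the count unless the table also shows the Day 0 grade.

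**The case against.** Several points can fairly be made for the plan.

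- **Inclusion of Day 0 is inferred.** The text says across visits and does not name Day 0. The programming specifications and table shells (SAP 5.7) are not in the documents and may exclude it. This stands as a limit on certainty, but the written rule contains no exclusion, and a programmer following it would include Day 0.
- **Other outputs show Day 0.** The by-visit summaries and the by-visit LSR listing let a reader compare Day 0 with later visits, and drug-related adverse events in the treatment area have their own table (14.3.1.9). This stands, and it confines the problem to Table 14.3.2.2. By-visit counts alone cannot, however, give each subject's worst grade after baseline, and the change from baseline in SAP 5.5.4 is for sum scores, not for single signs.
- **Day 0 signs may be rare.** Exclusion criterion 12 bars atrophic skin, atrophic striae, ulcers and infections in the treatment area, so a high prevalence is implausible for atrophy and erosion/ulceration. This stands for those categories. The criterion does not name perilesional erythema, scaling or edema.
- **The calculation is binary.** The table shows the distribution of grades, so a subject at grade 1 on Day 0 who worsens to grade 2 or 3 is still recorded at the worse grade. This stands.

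A reader might infer that the rule hides a safety difference between cream, gel and vehicle, or weakens a trial conclusion. The documents do not support that. SAP 5.5.5 makes the safety analyses descriptive and exploratory, no test or step in the testing hierarchy uses LSR, and no figure for Day 0 signs is given.

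**Conclusion.** The definition should be corrected. As written, a sign present only before treatment counts as that subject's most intense reaction, contrary to how the plan treats adverse events, protocol laboratory extremes and notable vital signs. The consequence is limited to inflated frequencies and diluted arm differences in Table 14.3.2.2.

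The size depends on two unknowns: how common each sign is at Day 0, and how many of those signs resolve. Under the assumed 6% versus 3%, with independent new reactions and full resolution, the tabulated ratio lies between 2.0 (no Day 0 signs, no effect) and 1.04 (40% prevalence). With full persistence, the choice between the two maxima makes no difference. These figures show the range and are not an estimate for this trial. Confidence is high that the restriction is missing from the text, and low about how much it would change the table.

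**What to change.** In SAP 2.4.2, define the most intense reaction for each area and sign as the maximum grade over visits after the first application: Weeks 1, 4, 6 and 8/early termination, and any unscheduled visit with an LSR assessment. Naming the area matters because vesicles and erosion/ulceration are graded in both lesional and perilesional skin.

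Present Table 14.3.2.2 as a shift table, Day 0 grade by worst post-baseline grade, per arm. Resolved, persistent and worsened signs are then all visible. Counting only grades above Day 0 would be a weaker choice, because it drops reactions that persist unchanged.

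Record the clarification of Protocol 8.7.2 in SAP 5.6. A protocol amendment is not needed: Protocol 8.1 describes its methods as an overview to be detailed in the SAP.

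The cost is one SAP sentence, one entry in SAP 5.6 and a slightly larger table shell. All the data are already collected.
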